### 2.3 Exploratory Objectives

- (1) Characterize and compare peripheral blood immune cell phenotypes before and after metformin, pembrolizumab and combination treatment with a particular focus on Natural Killer (NK) cells and innate immunity.
- (2) Characterize and compare tumor infiltrating NK cells before and after metformin, pembrolizumab and combination treatment.
- (3) Determine cytokine levels before and after metformin, pembrolizumab and combination in the plasma.
- (4) Determine NK effector functions before and after metformin, pembrolizumab and combination.
- (5) Determine Stat-3 RNA levels and phosphorylation status in NK cells and tumor tissue before and after metformin, pembrolizumab and combination treatment.
- (6) Evaluate NKG2D soluble ligands before and after metformin, pembrolizumab and combination in the plasma.

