## Specimen Collection Schedule

Specimen Type	Pre-treatment Day -14 (Arm 1) Day -21 (Arm 2)	Cycle 1 Day 1 (Arm 1); Day -7 (Arm 2)	Cycle 2 Day 1 (Week 4)
Peripheral Blood 60mls in 6 EDTA tubes and 5mls in 1 red top serum tube	X	X	X
FFPE slides x 20 and 1 tissue scroll	X		X

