Scatter plots and histograms will be used to examine the exploratory endpoints for the presence of unusual outliers, normality and potential non-linearity. Continuous endpoints will be log-transformed if not normally distributed. The endpoints using samples before and after treatment will be compared using paired T tests. When endpoints are compared between three or more groups, ANOVA model will be used. The ANOVA will be followed up with post-hoc pairwise comparisons. A chi-square test will be used to investigate the categorical exploratory endpoints. For IHC, the percentage of positive cells per area will be multiplied by the staining intensity for each tumor to determine quantitative expression pre- and post-treatment.

To detect a difference of 15% in %NK Cell Killed Target Cells between control and treated groups,

we will need 19 pairs of patients. In an unpaired comparison, 10 patients per group will give us enough power to detect a difference of at least 30% between the groups. We note that the average %NK Cell Killed Target Cells in controls was assumed to be around 10% (Data not shown) and the standard deviation was estimated from the range of 5 to 15%. We also note that the calculations are based on the significance threshold of 0.05 and an 80% detection power using one-sided tests.

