### 10.4 Randomization:

Patients will be randomized into arms 1 and 2 using R (R Core Team. 2012) at time of registration (if screening labs are to be obtained on same day as treatment randomization may be performed at the time all other eligibility criteria are informally confirmed to allow adequate time for treatment planning). The UC Project Manager will work with the statistician to ensure each patient is assigned to one of the arms correctly. Randomization of patients does not affect the primary or secondary endpoints of this study as response and safety is based on the combination treatment in which both groups will receive. The patients are randomized for the exploratory endpoints in order to better understand the difference of effects of metformin versus pembrolizumab on the immune system.

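### Serial blood comparisons across three or more states need a model with a patient effect, and the randomised arm contrast should use the pre-treatment sample; the plan specifies neither (exploratory endpoints only)

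*Combined protocol and SAP*

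**What the plan says.** Section 10.1 has three analysis rules for the exploratory endpoints.

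- Two samples from one patient: "The endpoints using samples before and after treatment will be compared using paired T tests".
- More than two groups: "When endpoints are compared between three or more groups, ANOVA model will be used", and then "The ANOVA will be followed up with post-hoc pairwise comparisons". The type of ANOVA (one-way or repeated-measures) is not stated.
- Categories: "A chi-square test will be used to investigate the categorical exploratory endpoints". No paired version is named.

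The first objective in Section 2.3 is to "Characterize and compare peripheral blood immune cell phenotypes before and after metformin, pembrolizumab and combination treatment". Section 5.1 assigns each patient to one of two arms. The Specimen Collection Schedule in Section 6.1 takes blood three times (before treatment, after the single-agent lead-in, at Cycle 2 Day 1) and tissue twice. Footnote h of the Study Calendar (Section 12) makes the pre-treatment blood sample a condition for the later ones. Section 10.4 explains the allocation: "The patients are randomized for the exploratory endpoints in order to better understand the difference of effects of metformin versus pembrolizumab" on the immune system.

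**The concern.** With only two arms, a comparison of three time points, or of metformin alone, pembrolizumab alone and combination, must use some patients more than once. An ANOVA that treats the samples as independent leaves between-patient variation in the error term. Intervals are then too wide, p-values too large, and real immune changes can be missed.

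A separate question is how the two arms are compared after the lead-in. That is the comparison for which patients are randomised. A pre-treatment value is required from everyone who contributes later blood samples, yet no analysis is said to use it. At stake is the yield of the immune sub-study. The response, safety and survival endpoints are untouched.

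**Working it through.** **Inputs.** From Section 10.1: control mean 10%, range 5 to 15%, differences of 15% (paired) and 30% (unpaired), and "calculations are based on the significance threshold of 0.05 and an 80% detection power using one-sided tests". From Section 10.2: 19 evaluable patients. The SD is not stated; I infer range/4 = (15 − 5)/4 = 2.5. I read the differences as relative to the mean, giving 1.5 and 3.0 points. Allocation is assumed 1:1.

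**1. The plan's own figures.** Noncentral t, one-sided 0.05:

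- Paired: 1.5/2.5 = 0.6. Power is 0.787 with 18 pairs and 0.808 with 19, so 19 pairs reproduces.
- Unpaired: 3.0/2.5 = 1.2. Power is 0.785 with 9 per group and 0.825 with 10, so 10 per group reproduces.

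The paired result uses 2.5 as the SD of a difference. If one measurement also has SD 2.5, then 2.5² = 2 × 2.5² × (1 − ρ), so ρ = 0.5. The documents give no correlation, so ρ is an assumption throughout.

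**2. Interval width.** For the difference between two time points, the independent-samples SE divided by the paired SE is 1/√(1 − ρ): 1.41 at ρ = 0.5 and 1.83 at ρ = 0.7.

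**3. Three time points, ordinary versus repeated-measures ANOVA.** Simulation with normal data, equal correlations, 5% F tests, and means 0, 0.3 and 0.6 SD (a total shift of 1.5 points):

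| Patients | ρ | Ordinary: true size | Ordinary: power | Repeated-measures: power |
|---|---|---|---|---|
| 19 | 0.3 | 1.6% | 0.29 | 0.46 |
| 19 | 0.5 | 0.4% | 0.25 | 0.61 |
| 19 | 0.7 | under 0.1% | 0.19 | 0.83 |
| 10 | 0.5 | 0.6% | 0.10 | 0.33 |

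Repeat simulations of the 19-patient, ρ = 0.5 case put the size between 0.3% and 0.45%. The 19-patient rows treat the lead-in as one common state, but it is metformin in Arm 1 and pembrolizumab in Arm 2, so the 10-patient row is closer to a single-drug series. With means 0, 1.5 and 3.0 points and ρ = 0.5, power is 0.95 versus nearly 1.00 with 19 patients, and 0.61 versus 0.89 with 10.

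**4. Metformin, pembrolizumab and combination as three groups.** With 10 metformin-alone, 9 pembrolizumab-alone and 19 combination samples from the same 19 patients, ordinary ANOVA has true size 2.3% (ρ = 0.5) or 1.8% (ρ = 0.7).

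**5. The randomised contrast.** The two arms are different people, so an unpaired test is valid. Baseline adjustment multiplies the residual SD by √(1 − ρ²): 0.866 at ρ = 0.5 (13% lower) and 0.714 at ρ = 0.7 (29% lower). One-sided power with 10 per arm:

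- 1.5 points: 0.36 unadjusted; 0.42 (ρ = 0.5) to 0.54 (ρ = 0.7) adjusted.
- 3.0 points: 0.83 unadjusted; 0.89 to 0.97 adjusted.

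The adjusted figures allow for chance baseline imbalance between the arms. Ignoring it gives 0.44 to 0.56 and 0.91 to 0.98.

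**6. Categories.** Splitting 19 patients 10/9, the smallest expected count in any 2×2 table of arm by outcome is at most 9 × 9/19 = 4.3, below the usual minimum of 5. For paired categories (19 patients, 30% in both samples, latent correlation 0.5) an unpaired chi-square has true size of about 2%. For 30% versus 60%, its power is 0.47, against 0.57 for asymptotic McNemar, 0.54 for mid-p and 0.41 for exact McNemar.

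**The case against.** The strongest reply is that the plan does respect pairing. Before/after samples get paired t tests, and most exploratory objectives are worded as before/after. This stands, and it fully covers tissue, which is sampled only twice.

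Second, the plan says only that an ANOVA model is used, and repeated-measures ANOVA is one. Some comparisons of three groups involve separate patients: Sections 3.4 and 6.1 relate immune markers to clinical response, and response categories are independent groups. Nor is chi-square assigned to pre/post categories. This also stands: the defect is an omission, not a stated wrong test. But classical repeated-measures ANOVA would not fit the metformin/pembrolizumab/combination comparison either, because no patient supplies both single-agent states.

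Third, a reader might infer that the randomised comparison loses most of its power. The documents do not support that. The large losses belong to within-patient contrasts with small effects; the randomised contrast is between independent patients, and omitting baseline costs what step 5 shows. The sentence about 10 patients per group is a power statement and does not exclude adjustment or change from baseline.

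A reader might also infer false-positive risk. Pooling each patient's three samples as independent to compare arms would raise a one-sided 5% to about 12% at ρ = 0.5, but nothing says this will be done.

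Finally, Section 10.4 states that randomisation does not affect the primary or secondary endpoints, and no stopping or success rule rests on these tests.

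**Conclusion.** The point holds as a gap in specification for the serial blood endpoints. If the ANOVA is run as an ordinary one, it is conservative and costs power, heavily for small shifts and within one arm, little for large shifts in 19 patients. The randomised contrast is valid as an unpaired test but leaves the pre-treatment sample unused, a moderate loss. Chi-square is poorly suited to the expected counts between arms and, if applied to paired categories, ignores the pairing.

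The sizes rest on correlations of 0.3 to 0.7 that the documents do not give, an SD of 2.5 inferred from the range, equal correlations between time points, an intermediate mean halfway between the first and last, and 1:1 allocation. The direction does not depend on these values as long as samples from one patient are positively correlated, except that baseline adjustment gains little when that correlation is low. Only exploratory endpoints are affected. The change is still worth making, since these endpoints are the stated reason for randomising.

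**What to change.** In Section 10.1, for the serial blood endpoints:

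- Use a linear mixed model on the (log) values with a patient random effect and arm, time and arm-by-time terms. Pre-specify the contrasts: lead-in versus pre-treatment within arm, combination versus lead-in, and combination versus pre-treatment pooled over arms. The model also keeps patients with incomplete series, which matters because the summary of changes reports more withdrawals than expected in Arm 2.
- Make the randomised contrast the arm difference in the post-lead-in value adjusted for the pre-treatment value (ANCOVA).
- State the assumed within-patient correlation and SD.

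Keep paired t tests for the two-time-point tissue endpoints and ordinary ANOVA for truly independent groups, such as response categories. Use Fisher's exact test between arms and exact McNemar for any paired categories. The reason for exact McNemar is validity with paired data, not power: at 19 patients it is itself conservative, and the mid-p version recovers most of the loss.

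The cost is a few sentences of analysis text and a few lines of code. No new samples, visits or patients are needed.

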## 10.2 Sample Size/Accrual Rate

We expect that metformin and pembrolizumab combination therapy will improve ORR to 32%. Our preliminary sample size calculations indicate that 25 patients should be enough to approximately estimate the proportion of around 32% with a margin of error close to 20%. We note that ORR of pembrolizumab alone based on previous clinical studies varies between 15-20% in HNSCC; and retrospective studies show metformin increased response rates by about 10-15% in other tumor types. We also note that the calculations are based on the significance threshold of 0.05 and an 80% detection power using one-sided tests. We plan to enroll twenty-five patients total with goal of 19 evaluable (20% expected drop-out rate given dysphagia seen in head and neck cancer patients). If 6/19 achieve response, we will consider study successful and worth pursuing further in a phase II/III study. The above calculations are based on the significance threshold of 0.05 and using the critical values of the normal distribution. We expect to enroll the patients over 18-24 months.

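### The 80% power for 10 patients per group rests on a one-sided treated-versus-control test; for the randomised metformin-versus-pembrolizumab contrast, which has no stated direction, two-sided power is about 72%

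*Combined protocol and SAP*

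**What the plan says.** Section 10.1 gives two sample sizes for the percentage of target cells killed by NK cells. The paragraph opens with "To detect a difference of 15% in %NK Cell Killed Target Cells between control and treated groups", for which it asks for 19 pairs, and then states: "In an unpaired comparison, 10 patients per group will give us enough power to detect a difference of at least 30% between the groups". On the inputs it says that "the average %NK Cell Killed Target Cells in controls was assumed to be around 10" percent and that "the standard deviation was estimated from the range of 5 to 15" percent. On the error rates it says that "the calculations are based on the significance threshold of 0.05 and an 80% detection power using one-sided tests".

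Section 10.4 explains that both arms receive the combination, that randomisation does not bear on the primary or secondary endpoints, and that patients are randomised for the exploratory endpoints "in order to better understand the difference of effects of metformin versus pembrolizumab on the immune system".

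The specimen schedule in section 6.1 and the study calendar show how that contrast would be made. Arm 1 is sampled before treatment on Day -14 and, after the metformin lead-in, on Day 1. Arm 2 is sampled before treatment on Day -21 and, after the pembrolizumab lead-in, on Day -7.

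For numbers, section 10.2 says: "We plan to enroll twenty-five patients total with goal of 19 evaluable". The analysis methods in 10.1 name paired t tests, ANOVA with post-hoc pairwise comparisons, and chi-square tests. They give no test and no sidedness for Arm 1 against Arm 2.

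**The concern.** A one-sided test needs a direction fixed in advance. Treated against control has a natural one: treatment should raise NK killing. The contrast for which patients are randomised does not, because after the lead-in both arms are on an active drug. The hypotheses in section 3.4 that carry a direction concern change after metformin or the gain from the combination. None says that one drug alone should exceed the other.

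If the contrast is tested two-sided, the critical value rises and the power at 10 per group falls below the 80% in the text. At stake is how much weight a null arm comparison can bear. A reader who takes the printed 80% at face value would give it more than the design supports. The contrast is also the only reason the protocol gives for randomising, so its test and its power should be stated for what it is.

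**Working it through.** **Inputs**

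- Control mean 10%, range 5 to 15%, alpha 0.05 one-sided, power 80%, 19 pairs, 10 per group: section 10.1.
- SD: not printed. Assumed to be range/4 = (15 − 5)/4 = 2.5 points.
- Differences: read as relative. 30% of 10 = 3.0 points; 15% of 10 = 1.5 points.
- Standardised differences: 3.0/2.5 = 1.2 unpaired; 1.5/2.5 = 0.6 paired, taking 2.5 as the SD of the paired differences.

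**Step 1. Reproduce the plan's figures (t tests, noncentral t)**

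- Unpaired: noncentrality = 1.2/√(1/n₁ + 1/n₂). At 10 v 10 it is 1.2/√0.2 = 2.683, with 18 degrees of freedom and one-sided critical value 1.734. Power is 82.5%. At 9 v 9 power is 78.5%, so 10 is the smallest adequate size, as printed.
- Paired: noncentrality = 0.6·√19 = 2.615, with 18 degrees of freedom. Power is 80.8%. With 18 pairs it is 78.7%, so 19 is the smallest adequate size, as printed.

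Other readings do not fit. Range/6 (SD 1.67) gives 5 per group and 10 pairs. Range/√12 (SD 2.89) gives 13 and 25. Range/2 (SD 5) gives 36 and 71. An absolute 30-point difference would have power near 100% at 10 per group. The two inferred inputs are therefore well supported.

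**Step 2. Same inputs, two-sided at 0.05**

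At 10 v 10 the noncentrality stays at 2.683, but the critical value becomes 2.101.

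| Usable samples (Arm 1 v Arm 2) | One-sided power | Two-sided power |
|---|---|---|
| 10 v 10 | 82.5% | 71.8% |
| 9 v 10 | 80.5% | 69.2% |
| 12 v 12 | 88.5% | 80.2% |
| 12 v 13 | 89.7% | 81.9% |

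The 9 v 10 row splits the 19 evaluable patients of section 10.2 about equally, and the 12 v 13 row splits all 25 enrolled. The allocation ratio is not stated, so both splits are assumptions. At 10 v 10 the difference detectable two-sided with 80% power is 3.31 points, or 33% of the control mean.

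**Step 3. Effect of adjusting for the pre-treatment value**

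Approximate the adjusted SD by 2.5·√(1 − ρ²) and remove one degree of freedom (17 at 10 v 10, critical value 2.110). The within-patient correlation ρ is not in the documents, so a range is shown.

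| Assumed ρ | Adjusted SD | Two-sided power, 10 v 10 | Two-sided power, 9 v 10 |
|---|---|---|---|
| 0.3 | 2.385 | 75.5% | 72.9% |
| 0.5 | 2.165 | 83.1% | 80.8% |
| 0.7 | 1.785 | 94.3% | 92.9% |

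**The case against.** The best defence is that nothing in section 10.1 is miscalculated. The one-sided basis is stated openly and both sample sizes follow from it. A two-sample t calculation is the same for drug against drug as for treated against control, so a reader who infers an arithmetic error, or a formula for the wrong design, goes too far. Only the sidedness is at issue. This stands.

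The unpaired sentence also never names Arm 1 against Arm 2. Nor is that the trial's only between-patient comparison: section 10.1 plans ANOVA across three or more groups, and section 6.1 plans to study whether tissue biomarkers predict response. It is the only randomised between-arm contrast, and the claim here is limited to that.

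A reader might infer that 80% power cannot be reached. The documents do not show this. The 19 evaluable is set for response, and the lead-in blood samples do not depend on response evaluability. The summary of changes attributes the increase to 25 to withdrawal on Arm 2 before metformin was started or reached steady state. The Arm 2 contrast sample falls on the day metformin starts, so some of those patients could still supply it. With 12 per arm, power is 80.2%. Against that, the NK cytotoxicity assay is optional in section 6.1, and by calendar note h a missed pre-treatment sample ends blood collection for that patient. Near-complete sampling cannot be assumed.

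It is also tempting to set the 15% in the paired sentence against the 30% in the unpaired one and conclude that real power is far lower. Both are detectable differences, for two different designs. Neither is put forward as the expected gap between the drugs, so the documents support no such conclusion. Nor do they suggest that a test direction would be chosen after seeing the data.

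**Conclusion.** The point holds as a mismatch between the stated basis and the contrast for which patients are randomised. The printed 10 per group is correct on its own one-sided terms, but those terms are not justified for metformin alone against pembrolizumab alone. Tested two-sided, power at 10 per arm is about 72%, some 8 points below the stated 80%. The range is 69% at 9 v 10 to 82% if all 25 patients give usable samples.

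This rests on an inferred SD of 2.5 points, a relative reading of the 30%, and roughly equal allocation. The first two are corroborated by both printed sample sizes. Severity is minor: the assay is exploratory and optional, no decision rule depends on it, and the primary and secondary endpoints are untouched.

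**What to change.** In section 10.1:

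1. Name the arm contrast (Arm 1 post-lead-in, Day 1, against Arm 2 post-lead-in, Day -7) and state that it is tested two-sided at 0.05.
2. Restate its unadjusted power as about 72% at 10 per arm for a 30% relative difference, with about 33% as the difference detectable at 80% power. State the SD of 2.5 points and the relative scale, if these are what was used.
3. Analyse it by ANCOVA of the post-lead-in value on arm and the pre-treatment value (Day -14 or Day -21). Quote power of about 76%, 83% and 94% at 10 per arm for correlations of 0.3, 0.5 and 0.7, labelled as assumptions.

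The one-sided wording can stay with the treated-versus-control calculation, where a direction exists. The change needs no new patients or samples. It costs a less favourable unadjusted figure and one degree of freedom.

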## 10.2 Sample Size/Accrual Rate

We expect that metformin and pembrolizumab combination therapy will improve ORR to 32%. Our preliminary sample size calculations indicate that 25 patients should be enough to approximately estimate the proportion of around 32% with a margin of error close to 20%. We note that ORR of pembrolizumab alone based on previous clinical studies varies between 15-20% in HNSCC; and retrospective studies show metformin increased response rates by about 10-15% in other tumor types. We also note that the calculations are based on the significance threshold of 0.05 and an 80% detection power using one-sided tests. We plan to enroll twenty-five patients total with goal of 19 evaluable (20% expected drop-out rate given dysphagia seen in head and neck cancer patients). If 6/19 achieve response, we will consider study successful and worth pursuing further in a phase II/III study. The above calculations are based on the significance threshold of 0.05 and using the critical values of the normal distribution. We expect to enroll the patients over 18-24 months.

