a combination of a platinum (cisplatin or carboplatin), fluorouracil and Cetuximab (an epidermal growth factor receptor inhibitor). Although adding Cetuximab to platinum-based chemotherapy significantly extended median overall survival (OS) to 10.1 months from 7.4 months with chemotherapy alone, the rate of grade 3 or 4 adverse events was high at 82% for the combination. Therefore, other platinum-based regimens such as carboplatin and paclitaxel are often used to reduce toxicity. Success in the second line setting after failure of platinum therapy is even more dismal with median OS rates around 5-6 months. More recently, immunotherapy has been shown to significantly increase survival rates in a handful of R/M HNSCC patients. In fact, the PD-1 checkpoint inhibitors, Pembrolizumab and Nivolumab, are both now FDA approved after failure of platinum therapy in the recurrent/metastatic setting. Keynote 40, comparing Pembrolizumab to standard of care chemotherapy (methotrexate, docetaxel or Cetuximab) after failure to platinum therapy, demonstrated that although the primary endpoint was not reached, there was a clinically meaningful increase in overall survival for Pembrolizumab at 8.4 months (95% CI 6.4–9.4) compared to 6.9 months (5.9–8.0) with standard of care (hazard ratio 0.80, 0.65–0.98; nominal  $p=0.0161$ ). Nivolumab was also found to be superior in overall survival compared to standard of care chemotherapy in Checkmate 141 (hazard ratio for death, 0.70; 97.73% CI, 0.51 to 0.96;  $P=0.01$ ) establishing immunotherapy as the new standard of care after platinum failure in HNSCC. Recently, Pembrolizumab was found to be superior to the extreme regimen in the first line setting of metastatic/recurrent HNSCC as well. Pembrolizumab alone is now FDA approved for first line R/M HNSCC patients with a CPS score of  $\geq 1$  and combination of pembrolizumab, platinum and 5-FU for those with CPS  $<1$ . Importantly, combination of chemotherapy and immunotherapy had similar rates of toxicity to the Extreme regimen limiting its use. Despite the progress and impressive durable responses seen with immunotherapy in recurrent and metastatic HNSCC, the response rates remain low at 18-22%. Several subsequent studies have been performed to show that patients with high tumor mutational burden (TMB), increased PD-L1/L2 expression and Interferon gamma (IFN- $\gamma$ ) signatures are more likely to respond to immunotherapy. However, mechanisms of resistance and more importantly, therapies likely to overcome immunotherapy resistance with low toxicity are lacking.

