## STATISTICAL CONSIDERATIONS

### 10.1 Study Design/Endpoints

Primary Endpoint: Overall Response by RECIST 1.1 and iRECIST

Responses will be summarized as frequencies and percentages.

Secondary Endpoints:

- Measurement of Adverse Events by CTCAE v5.0
- Progression Free Survival (PFS) at 1 year
- Overall Survival (OS) at 1 year

After cleaning and preprocessing of the collected data, descriptive statistics will be used to summarize all adverse events. Toxicities will be aggregated as the number and percentage of patients with each type of toxicity. Kaplan Meier methods will be used to estimate overall survival and progression free survival generating median survival estimates with 95% confidence intervals (95% CIs). Multivariable survival modeling (overall survival and progression free survival) will be performed using Cox proportional hazards models and to generate Hazard Ratios (HR) and 95% CIs, with adjustment for potential patient confounders such as age, sex, smoking status, etc.

Exploratory Endpoint:

- Characterization of peripheral blood immune cell phenotypes before and after metformin, pembrolizumab and combination treatment with a particular focus on Natural Killer (NK) cells and innate immunity.
- Characterization of tumor infiltrating NK cells before and after metformin, pembrolizumab and combination treatment.
- Cytokine levels before and after metformin, pembrolizumab and combination in the plasma.
- NK effector functions before and after metformin, pembrolizumab and combination.
- Stat-3 RNA levels and phosphorylation status in NK cells and tumor tissue before and after metformin, pembrolizumab and combination treatment.
- Level of NKG2D soluble ligands before and after metformin, pembrolizumab and combination in the plasma.

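### Section 10.2 states 80% power at a one-sided 0.05 threshold but names no null ORR, and its only decision rule, 6 responses in 19, has 60% power at the target of 32%

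*Combined protocol and SAP*

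**What the plan says.** Section 10.2 (Sample Size/Accrual Rate) expects the combination to reach an ORR of 32%. It justifies the sample size by precision: "25 patients should be enough to approximately estimate the proportion of around 32% with a margin of error close to 20" percent. For comparison it says that "ORR of pembrolizumab alone based on previous clinical studies varies between 15-20% in HNSCC". It continues: "We also note that the calculations are based on the significance threshold of 0.05 and an 80% detection power using one-sided tests". It then plans 25 enrolled and 19 evaluable with 20% drop-out, and gives the decision rule: "If 6/19 achieve response, we will consider study successful and worth pursuing further in a phase II/III study". The next sentence reads: "The above calculations are based on the significance threshold of 0.05 and using the critical values of the normal distribution".

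Two other places bear on this. Section 3.1 says of immunotherapy in this disease that "the response rates remain low at 18-22" percent. Section 10.1 plans no test and no confidence interval for the primary endpoint: "Responses will be summarized as frequencies and percentages".

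**The concern.** A significance level and a power mean something only for a stated null rate, alternative and decision rule. Section 10.2 supplies the alternative (32%) and a rule (6 of 19), but no single null. A reader will naturally attach 0.05 and 80% to that rule, because it is the only criterion for success on ORR in the section. If the rule does not have those properties, the team that decides on a phase II/III study will misjudge two things: how often an active combination would meet the criterion, and how often pembrolizumab-like activity alone would meet it.

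**Working it through.** **Inputs.** From 10.2: cut-off 6, evaluable n = 19, target ORR 32%, reference rates 15% to 20%, one-sided 0.05, 80% power, normal critical values, 25 enrolled, 20% drop-out. From 3.1: 18% to 22%. I read the rule as at least 6 responses.

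**1. The plan's precision figure.** Half-width = 1.96 × √(0.32 × 0.68 / n). This gives 18.3 points for n = 25, 20.4 for n = 20 and 21.0 for n = 19. The stated margin of about 20 points reproduces.

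**2. The rule, exact binomial.** P(X ≥ 6), X ~ Bin(19, p):

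| True ORR | P(go) |
|---|---|
| 15% | 0.054 |
| 18% | 0.111 |
| 20% | 0.163 |
| 22% | 0.225 |
| 32% | 0.601 |

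The 0.601 does not depend on any choice of null. The rule reaches 80% only at a true ORR of about 38.5%.

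**3. The rule, normal approximation.** Since 10.2 cites normal critical values, take z = (6 − 19p) / √(19p(1 − p)), or 5.5 in place of 6 with continuity correction. At p = 0.15, z = (6 − 2.85)/1.556 = 2.02, so P = 0.021 (0.044 corrected). At 18% it is 0.062 (0.107), and at 20% it is 0.104 (0.165). At 32% it is 0.516 (0.612). So the level is met at 15% by this method and exceeded at 18% and above. Power stays near 50% to 60%.

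**4. Could another test carry the 80%?** One-sample normal test, one-sided 0.05:

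Power = Φ{[(0.32 − p0) − 1.645√(p0(1 − p0)/n)] / √(0.32 × 0.68/n)}

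| n | p0 = 15% | p0 = 18% | p0 = 20% |
|---|---|---|---|
| 19 | 0.629 | 0.481 | 0.386 |
| 20 | 0.645 | 0.495 | 0.397 |
| 25 | 0.713 | 0.558 | 0.451 |

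The most favourable cell (n = 25, p0 = 15%) is [0.17 − 1.645 × 0.0714]/0.0933 = 0.563, and Φ(0.563) = 0.713. None reaches 0.80.

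For scale, 80% power against 32% at one-sided 0.05 needs about 34 evaluable patients (normal) or 38 (exact) if p0 = 15%, 54 or 58 if 18%, and 77 or 85 if 20%.

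**5. Evaluable number.** 25 × 0.80 = 20, and 1 − 19/25 = 24%, so 20% drop-out and 19 evaluable differ by one patient. Section 13.1.1 makes evaluability depend on measurable disease, one cycle received and a re-evaluation, so the final count may not be 19. With the cut-off held at 6 (17 is my illustration of a shortfall):

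| Evaluable | P(go) at 20% | P(go) at 32% |
|---|---|---|
| 17 | 0.106 | 0.475 |
| 19 | 0.163 | 0.601 |
| 20 | 0.196 | 0.657 |
| 25 | 0.383 | 0.859 |

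A cut-off of 6 in all 25 does pass 80% power, but only with a false-go rate of 16% at 15% and 38% at 20%.

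**6. Cut-offs for an exact one-sided 0.05 test, n = 19.** Against 15% or 18% the cut-off is 7 (level 0.016 or 0.041; power 0.407). Against 20% it is 8 (level 0.023; power 0.238).

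**The case against.** The strongest defence is that 10.2 never says the 6/19 rule has 0.05 and 80%. The sentence with 80% refers to the calculations in general and comes before the rule. The calculation described ahead of it is one of precision, which reproduces. The sentence after the rule repeats 0.05 but not 80%. The same 80%, one-sided sentence also closes the NK-cell killing calculation in 10.1, so it may have been carried over. The trial is small and ORR is only to be described. This stands in part: the firm defect is a power statement with no named hypothesis, not a proven promise about 6/19. It does not remove the problem. Carry-over cannot be shown from the documents, and if that is what happened, the sentence should not stand in the ORR section.

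Four stronger readings are tempting and are not supported:

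- **The rule misses 0.05 at every reference rate.** At 15% it is met by the plan's normal approximation (0.021 or 0.044) and missed only narrowly by the exact test (0.054). Likewise, whether an observed 6/19 excludes 15% depends on the method: the exact one-sided 95% lower bound is 14.7%, while inverting the normal score test gives 17.3%.
- **The false-go rate is 23% on the plan's own design rates.** That needs the 22% in 3.1, which is background on immunotherapy. Over 10.2's 15% to 20%, the range is 5% to 16%.
- **An active combination would be abandoned 40% of the time.** The plan defines success only. It has no rule that fewer than 6 responses ends development.
- **The precision claim is wrong.** Both 18.3 and 21.0 points are fairly described as close to 20. The only issue is that precision is quoted for 25 while the rule uses 19.

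**Conclusion.** The stated 80% power is not supported by anything in 10.2. At the target ORR of 32% the rule is met with probability 60%, a shortfall of 20 percentage points that holds whichever null is chosen. The best one-sided 0.05 normal test over 19 to 25 patients and 15% to 20% reaches 71%. The level cannot be judged at one value because no null is named: it is borderline at 15% and clearly above 0.05 at 18% (11.1%), 20% (16.3%) and 22% (22.5%).

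These figures assume independent responses with a common probability, at least 6 as the success criterion, and exactly 19 evaluable patients. The mismatch between 19 and 20 evaluable, and between precision for 25 and for 19, is minor. The stated power should be corrected, because this rule is what is meant to justify a phase II/III study.

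**What to change.** In 10.2:

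- Remove the 0.05 and 80% statement for ORR, or replace it with the rule's real properties: with 19 evaluable, P(at least 6) is 60% at 32%, and 5%, 11% and 16% at 15%, 18% and 20%.
- Name one reference rate and say why it was chosen over the others quoted in 10.2 and 3.1.
- Make drop-out and evaluable number agree (24% for 19, or 20 evaluable for 20%), and quote precision for the evaluable number (±21 points for 19).
- State how the rule applies when the evaluable number is not 19.
- If an exact one-sided 0.05 test is wanted with 19 evaluable, use 7 responses against 15% or 18% and state 41% power, or 8 against 20% and state 24% power.

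In 10.1, report ORR with an exact 95% confidence interval. For an observed 6/19 this is 12.6% to 56.6%.

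The cost is wording in two sections and less favourable stated figures. No extra patients or procedures are needed. Section 14.1 gives the coordinating investigator access to the data at all times. The reference rate and any new cut-off should therefore be dated and justified before responses are summarised. Restating the properties of the existing rule carries no such risk.
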